5.2.2 Subsequent Cycles

- absolute neutrophil count $\geq 1,000/\text{mcL}$
- total bilirubin $\leq 1.5 \times$ institutional upper limit of normal (ULN) (or $2.0 \times$ ULN in patients with documented Gilbert's Syndrome)
- AST(SGOT)/ALT(SGPT) $\leq 2.5 \times$ institutional ULN or $\leq 3 \times$ institutional ULN for participants with documented liver metastases
- Urine pregnancy test in women of child-bearing age every 4 weeks (+/- 1 week)

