5.5 Criteria for Taking a Participant Off Protocol Therapy

Duration of therapy will depend on individual response, evidence of disease progression and tolerance. In the absence of treatment delays due to adverse event(s), treatment may continue for indefinite number or until one of the following criteria applies:

1. Disease progression by RECIST 1.1 Criteria
Although the primary endpoint is ORR as defined by RECIST 1.1, patients may remain on protocol therapy until the time of disease progression by irRC criteria. The immune criteria allows treatment beyond initial radiographic worsening of disease in order to distinguish between pseudoprogression and true disease progression.
2. Participants who have attained a confirmed complete response (CR) and who have been treated for at least 24 weeks on protocol therapy and had at least four treatments with nivolumab beyond the date when the initial CR was declared. Participants who stop nivolumab with CR may be eligible for additional nivolumab therapy if they progress after stopping study treatment. This retreatment is termed the Second Course Phase Therapy, as summarized below.
3. Intercurrent illness that prevents further administration of treatment
4. Unacceptable adverse event(s). If the subject does not recover from his or her toxicities to tolerable Grade ≤ 2 within 6 weeks, the subject will have study treatment discontinued unless there is unequivocal evidence that the subject is benefitting. In this situation, a subject may be able to restart therapy with a dose reduction upon resolution of the toxicity and with agreement of the principal investigator / Sponsor.
5. Participant demonstrates an inability or unwillingness to comply with the oral medication regimen and/or documentation requirements. OR Significant noncompliance with the protocol schedule in the opinion of the investigator. OR Subjects who cannot tolerate the minimum protocol-specified dose of study treatment will have study treatment discontinued.
6. Participant decides to withdraw from the protocol therapy
7. General or specific changes in the participant's condition render the participant unacceptable for further treatment in the judgment of the treating investigator

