6 DOSING DELAYS/DOSE MODIFICATIONS

6.1 Dosing/Delays/Omission/Modification

- The descriptions and grading scales found in the revised NCI Common Terminology Criteria for Adverse Events (CTCAE) version 5.0 will be utilized for dose delays and dose modifications.
- If multiple adverse events are seen, administer dose based on the greatest reduction required for any single adverse event observed. Reductions apply to treatment given in the preceding cycle and are based on adverse events observed since the prior dose.
- If more than one of these apply, use the most stringent (i.e. the greatest dose reduction).
- Dosing interruptions are permitted in the case of medical / surgical events or logistical reasons not related to study therapy (e.g., elective surgery, unrelated medical events, patient vacation, and/or holidays). Participants held for these reasons require prior approval from the PI and should resume therapy within 6 weeks of the scheduled interruption. The reason for interruption should be documented in the participant's study record.

- If treatment is withheld > 8 weeks from the last dose of cabozantinib or nivolumab, the patient should discontinue study therapy.
- For management of AEs which can be clearly attributed to cabozantinib or nivolumab, independent dose modification for either agent is allowed as described. For AEs without clear attribution to either study treatment, management of toxicity should include dose modifications or delay of both agents.
- Participants who require dose delay should be re-evaluated weekly or more frequently if clinically indicated and resume dosing when re-treatment criteria are met.
- Delayed doses of nivolumab and cabozantinib should be administered as soon as the participant meets criteria to resume treatment. If a dose has been delayed, the participant should not wait until the next scheduled dosing date.
- Dosing interruptions will not impact assessments or cycle/day scheduling.
- Restarting of treatment after dose interruption must be discussed with the PI.
- In order to standardize the management of adverse events, treatment management algorithms recommended for utilization in this study are included in Appendix B.

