6.5 Hepatobiliary Disorders

It is recommended that participants with elevation of ALT, AST, and/or bilirubin have more frequent laboratory monitoring of these parameters. If possible, hepatotoxic concomitant medications should be discontinued in participants who develop increased values of ALT, AST, or bilirubin.

Guidelines in the following table should be used for dose modifications.

Transaminase elevation CTCAE v. 5.0	Intervention
\leq Grade 1 AST or ALT $>$ ULN to $3.0 \times$ ULN and/or Total bilirubin $>$ ULN – $1.5 \times$ ULN	Continue study treatment, monitor liver function tests (LFTs) weekly for at least 4 weeks
Grade 2 AST or ALT $>$ 3.0 to $</= 5.0 \times$ ULN and/or Total bilirubin $>$ ULN – $1.5 \times$ ULN to $</= 3 \times$ ULN	Hold cabozantinib and nivolumab Monitor LFTs at least twice weekly until return to baseline or Grade $</= 1$ Consider referral to a hepatologist If persistent $>$ 5 days, start prednisone 60 mg/day or equivalent. When LFTs resolve to baseline or Grade ≤ 1 and steroid dose is

Transaminase elevation CTCAE v. 5.0	Intervention
	
prednisone \leq 10 mg/day or equivalent, restart nivolumab and cabozantinib at a reduced dose.
 
* Permanently discontinue protocol therapy for conditions fulfilling Hy's law with elevations $>3 \times$ ULN of ALT or AST concurrent with $>2 \times$ ULN total bilirubin without other explanation

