
Grade 3 AST or ALT > 5.0 to $\leq 20.0 \times$ ULN and/or Total bilirubin $>$ ULN – $3.0 \times$ ULN to $\leq 10.0 \times$ ULN
	
Hold cabozantinib and nivolumab. Monitor LFTs every 48–72 hours until LFTs return to baseline or Grade ≤ 1 Consider referral to hepatologist and liver biopsy to establish etiology of hepatic injury Start prednisone 60 mg/day or equivalent With first occurrence:
 
 If LFTs do not resolve to Grade < 3 within 7 days, permanently discontinue nivolumab and continue holding cabozantinib. When LFTs resolve to baseline or Grade ≤ 1, taper steroids over ≥ 1 month. When steroid dose is prednisone \leq 10 mg/day or equivalent, restart Nivolumab and Cabozantinib at a reduced dose. Subjects receiving cabozantinib at a daily dose of 20 mg may be restarted at the same dose if deemed safe at the discretion of the principal investigator. 
If recurs: permanently discontinue nivolumab. If the subject was unequivocally deriving clinical benefit, the subject may be able to resume cabozantinib at reduced dose as determined by the investigator.
 
* Permanently discontinue protocol therapy for conditions fulfilling Hy's law with elevations $>3 \times$ ULN of ALT or AST concurrent with $>2 \times$ ULN total bilirubin without other explanation

Grade 4 AST or ALT $> 20.0 \times$ ULN and/or Total bilirubin $>$ ULN $10.0 \times$ ULN
	
Permanently discontinue nivolumab and hold cabozantinib and inform the principle investigator.
 
Obtain hepatology consult and liver biopsy to establish etiology of hepatic injury.
 
Start prednisone 60 mg/day or equivalent.
 
If LFT results do not decrease within 48 hours after initiation of systemic steroids, consider addition of an alternative immunosuppressive agent (e.g., mycophenolate) to the corticosteroid regimen.
 
If LFTs resolve to baseline or Grade ≤ 1, taper steroids over ≥ 1 month.

Transaminase elevation CTCAE v. 5.0	Intervention
	If the subject was unequivocally deriving clinical benefit, the subject may be able to resume cabozantinib at reduced dose as determined by the investigator.

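### The Hy's law permanent stop in Section 6.5 is printed for grade 2 and grade 3 liver toxicity but not for grade 4, where the investigator may resume cabozantinib; the grade 4 steroid start also differs from Appendix B

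*Combined protocol and SAP*

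**What the plan says.** **Section 6.5, grade 2 and grade 3 rows.** Each ends with an instruction that begins "Permanently discontinue protocol therapy for conditions fulfilling" Hy's law, defined as ALT or AST above 3 x ULN together with bilirubin above 2 x ULN and no other explanation. No upper limit is given.

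**Section 6.5, grade 4 row** (AST or ALT above 20 x ULN and/or bilirubin above 10 x ULN). The instruction is "Permanently discontinue nivolumab and hold cabozantinib and inform the principle investigator". The row requires a hepatology consult and a liver biopsy, starts prednisone 60 mg/day or equivalent, and tapers over at least a month once liver tests recover. For a patient who was clearly benefiting, "the subject may be able to resume cabozantinib at reduced dose as determined by the investigator". The Hy's law sentence is not in this row.

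**Section 6.1.** Three rules bear on a restart: "If more than one of these apply, use the most stringent (i.e. the greatest dose reduction"; "If treatment is withheld > 8 weeks from the last dose of cabozantinib or nivolumab, the patient should discontinue study therapy"; and "Restarting of treatment after dose interruption must be discussed with the PI". Section 6.1 also recommends the Appendix B algorithms.

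**Appendix B, hepatic algorithm footnote.** The recommended start for grade 4 hepatitis is methylprednisolone IV at 2 mg/kg/day. The appendix describes itself as guidance. The hepatic figure is not shown in the public copy.

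**The concern.** A permanent stop that applies to moderate combined liver injury should also apply to the most severe. In 6.5 the stop sits inside two row cells and not in a note to the table, and the grade 4 cell has its own, softer instruction on cabozantinib. An investigator who reads only the grade 4 row for a patient with very high transaminases and bilirubin finds a hold and a route back to cabozantinib, and nothing about Hy's law.

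Nivolumab is stopped permanently at grade 4 in any case, so what is at stake is re-exposure to cabozantinib. Section 7.1.1 lists raised ALT and AST in that drug's own profile, so it is a plausible cause of the injury.

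The steroid start is a separate and lesser point. The grade 4 row gives a flat oral dose, and the appendix that 6.1 recommends gives a weight-based intravenous one.

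**Working it through.** The plan states no figure to reproduce. The check compares table rows, followed by simple arithmetic.

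**1. Which rows print the stop.** The inputs are the 6.5 bands for ALT/AST (above 3 to 5, above 5 to 20, above 20 x ULN) and the bilirubin bands cut at the Hy's law limit (above 2 to 3, above 3 to 10, above 10 x ULN). Because the row criteria are joined by and/or, each value brings in the row for its own grade.

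| ALT/AST | Bilirubin >2–3 | Bilirubin >3–10 | Bilirubin >10 |
|---|---|---|---|
| >3–5 | stop in every applicable row | stop in every applicable row | stop beside grade 4 permission |
| >5–20 | stop in every applicable row | stop in every applicable row | stop beside grade 4 permission |
| >20 | stop beside grade 4 permission | stop beside grade 4 permission | no applicable row prints it |

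The total is 3 x 3 = 9 combinations: neither value grade 4, 2 x 2 = 4; exactly one grade 4, 2 + 2 = 4; both grade 4, 1. These are table cells, not patients. Grade 4 ALT/AST with bilirubin at or below 2 x ULN does not meet Hy's law and is outside this point.

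**2. What happens as values fall.** Section 5.2.2 requires bilirubin at or below 1.5 x ULN (2.0 in Gilbert's syndrome) and AST/ALT at or below 2.5 x ULN (3 with liver metastases) for later cycles. If the row follows the current value, a patient leaving the both-grade-4 cell misses every stop-printing row only if, at the first draw outside that cell, ALT/AST is already at or below 3 or bilirubin at or below 2. That needs a fall of more than 20/3 = 6.7-fold in ALT/AST, or more than 10/2 = 5-fold in bilirubin, between consecutive draws. Section 6.5 does not say whether the row follows the current value or is fixed by the worst one.

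**3. Whether the safeguards close the gap.**
- Hold limit: 8 x 7 = 56 days. If the taper (at least 1 month, 28–31 days) is completed first, restart remains open to a patient whose liver tests recover within 56 − 31 = 25 to 56 − 28 = 28 days of the last cabozantinib dose. Unlike rows 2 and 3, the grade 4 row sets no steroid-dose condition for restart; without one, the window is up to 56 days.
- Section 5.2.2 tests current laboratory values, not whether Hy's law was met earlier.
- Section 5.5 item 4 covers patients not recovered to grade 2 or less within 6 weeks, and then "the subject will have study treatment discontinued unless there is unequivocal evidence that the subject is benefitting".
- PI discussion (6.1), hepatology consult and biopsy (6.5), and handling potential drug-induced liver injury as an SAE (7.5) inform the decision but do not require discontinuation.

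**4. Steroid start.** Weights of 50–100 kg and a prednisone-to-methylprednisolone potency ratio of 1.0–1.25 are assumptions; the documents give neither.
- Appendix B footnote: 2 mg/kg x 50–100 kg = 100–200 mg/day methylprednisolone, or 100 x 1.0 = 100 to 200 x 1.25 = 250 mg/day prednisone-equivalent, against 60 mg/day in 6.5.
- Weight at which the two agree: 60/2 = 30 kg, or (60/1.25)/2 = 24 kg. No usual adult weight reconciles them.
- Within Section 6, grade 4 colitis (6.4) starts at 1–2 mg/kg/day IV and grade 4 renal toxicity (6.23) at 1.0–2.0 mg/kg/day. In 6.4, prednisone 60 mg/day is the grade 2 start for persistent or recurrent symptoms and the step-down at grades 3 and 4.

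**The case against.** The best defence is that the stop already covers grade 4. It has no upper limit and was probably meant for the whole table. The grade 3 cell itself prints the stop next to the same permission to resume cabozantinib, so the natural reading is that the mandatory sentence overrides the discretionary one. The same reading, with the tie-break in 6.1, settles the four mixed combinations in favour of stopping. The both-grade-4 state is usually passing, because values normally fall through bands whose rows print the stop. Nivolumab is off regardless, and several checks stand before any cabozantinib restart.

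Most of this stands, and it limits the point. A reader might infer that the plan deliberately treats the worst liver injury more leniently, or that it generally allows cabozantinib after Hy's law. The documents do not support either reading. What remains is that the override is nowhere stated. The tie-break is explained in terms of dose reduction and needs more than one applicable rule; with both values at grade 4 there is only one row.

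On steroids, the defence is that Appendix B is guidance, that its hepatic figure cannot be seen, and that the grade 4 row also brings in a hepatologist and considers further immunosuppression at 48 hours. That stands too. A reader might infer that 6.5 breaches a mandatory dose, or that 60 mg/day is only ever a step-down in this protocol. The first is unsupported because the appendix is only recommended; the second is contradicted by the grade 2 row of 6.4.

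**Conclusion.** The point holds as a small patient-safety wording correction. In one of nine qualifying table combinations no applicable row prints the Hy's law stop. In four more it is printed, and favoured, but not expressly placed above the grade 4 permission to resume. The practical exposure is a cabozantinib restart in a patient who met Hy's law with at least one grade 4 value. Existing safeguards reduce that exposure without removing it. The documents give no hepatic event rates, so no probability can be attached.

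The steroid mismatch is real at any usual adult weight, under the stated weight and potency assumptions. It is secondary: it lies between two pieces of guidance, and which dose is right is a clinical decision.

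Neither part affects the objective response rate design or its error rates.

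**What to change.** 1. In 6.5, move the Hy's law sentence out of the grade 2 and 3 cells into one rule for the whole table. State that it applies at grades 2, 3 and 4 and overrides any permission to resume cabozantinib.
2. Have the clinical team compare the grade 4 steroid start in 6.5 with the Appendix B footnote and the hepatic algorithm figure, choose one regimen, and state which text governs where the two differ.

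The cost is amendment wording only, with no added visits, tests or patients.

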6.6 Elevated Amylase and/or Lipase

Patients may develop symptomatic and/or radiographic evidence of pancreatitis, diabetes mellitus, or pancreatic dysfunction related to cabozantinib or nivolumab. Amylase and lipase should be checked if there is clinical suspicion for pancreatitis. Corticosteroids do not seem to alter the natural history of lipase/amylase elevations related to nivolumab.

Patients with symptomatic or radiographic pancreatitis should discontinue nivolumab and consider consulting a gastroenterologist for management.

Table: Management of elevated amylase and/or lipase

Grade	Management/ Next Dose for Cabozantinib and Nivolumab
≤3	For asymptomatic ≤ grade 3 lipase or amylase elevation, continue protocol therapy. Ensure that participants have associated symptoms consistent with pancreatitis, such as abdominal pain, or hyperglycemia or radiographic pancreatic inflammation.
4	Hold nivolumab and cabozantinib. Ensure that participants have associated symptoms consistent with pancreatitis, such as abdominal pain, or hyperglycemia or radiographic pancreatic inflammation. If patient remains asymptomatic, resume treatment when ≤ Grade 1.

6.7 Fatigue, Anorexia and Weight loss Disorders

Fatigue has been reported during treatment with cabozantinib and nivolumab, the dose modifications are recommended for both drugs. Common causes of fatigue such as anemia, deconditioning, emotional distress (depression and/or anxiety), nutrition, sleep disturbance, and hypothyroidism should be ruled out and/or these causes treated according to standard of care. Individual non-pharmacological and/or pharmacological interventions directed to the contributing and treatable factors should be given. Pharmacological management with psychostimulants such as methylphenidate should be considered after disease specific morbidities have been excluded. Dose reduction of study treatment should be considered when general or pharmacological measures have not been successful in reducing symptoms.

- For Grade ≥ 3 fatigue despite optimal management, hold nivolumab and cabozantinib. When fatigue improves to \leq Grade 2, resume treatment with nivolumab at the same dose and cabozantinib at one dose level reduction.

Anorexia and weight loss should be managed according to local standard of care including nutritional support. Pharmacologic therapy such as megestrol acetate should be considered for appetite enhancement.

- For Grade ≥ 3 anorexia and weight loss despite optimal management, delay therapy. Treatment with nivolumab and cabozantinib with one dose level reduction may be resumed when symptoms improve to grade ≤ 2 .

6.8 Stomatitis and Mucositis

Refer to Section 5.4 for guidance regarding supportive care of mucositis and stomatitis.

For **grade 2 mucositis or stomatitis that is subjectively tolerable**, continue cabozantinib and nivolumab in addition to providing supportive care.

For **grade 2 mucositis or stomatitis that worsens, lasts ≥ 10 days, or interferes with adequate nutrition (and supportive care is insufficient)**, continue nivolumab but delay cabozantinib until toxicity improves to grade ≤ 1 , then resume cabozantinib with one dose level reduction.

For **grade 3 mucositis or stomatitis that interferes with adequate nutrition (and supportive care is insufficient)**, continue nivolumab but delay cabozantinib until toxicity improves to grade ≤ 1 , then resume cabozantinib with one dose level reduction.

For **grade 4 mucositis or stomatitis that interferes with adequate nutrition (and supportive care is insufficient)**, discontinue cabozantinib permanently, resume nivolumab when toxicity improves to grade ≤ 1 .

6.9 Palmar-plantar erythrodysesthesia (PPE) syndrome

Palmar-plantar erythrodysesthesia syndrome (also known as hand-foot syndrome), skin rash (including blisters, erythematous rash, macular rash, skin exfoliation, dermatitis acneiform, and papular rash), pruritus, dry skin, and erythema have been reported in cabozantinib-treated participants. Refer to Section 5.4 for guidance regarding supportive management of skin toxicity.

Management of Hand-Foot Syndrome (PPES) Associated with Cabozantinib

CTCAE v.5.0 Grade	Action To Be Taken
Grade 1	Cabozantinib treatment may be continued at the current dose if PPES is clinically insignificant and tolerable. Otherwise, cabozantinib should be reduced to the next lower dose level. ^a Start urea 20% cream twice daily AND clobetasol 0.05% cream once daily. Reassess at least weekly; if PPES worsens at any time or does not improve after 2 weeks, proceed to the intervention guidelines for Grade 2. Maintain dosing of nivolumab.
Grade 2	Cabozantinib treatment may be continued if PPES is tolerated. Cabozantinib should be dose reduced or interrupted if PPES is intolerable. Continue urea 20% cream twice daily AND high potency steroid cream (eg, clobetasol 0.05%) once daily and add analgesics (eg, NSAIDs/gamma-aminobutyric acid agonists) for pain control if needed. Reassess at least weekly; if PPES worsens or affects self-care or is intolerable, proceed to the intervention guidelines for Grade 3. Maintain dosing of nivolumab.
Grade 3	Interrupt cabozantinib treatment until severity decreases to Grade 1 or 0. Continue treatment of skin reaction with high potency steroid cream (eg, clobetasol 0.05%) twice daily AND analgesics. Resume study drug at a reduced dose if PPES recovers to Grade ≤ 1 . Discontinue subject from study treatment if PPES does not improve within 6 weeks. Maintain dosing of nivolumab.

CTCAE, Common Terminology Criteria for Adverse Events; NSAID, non-steroidal anti-inflammatory drug; PPES, palmar plantar erythrodysesthesia syndrome.

^a Permitted dose levels are defined by individual protocols.

6.10 Other dermatologic disorders

Treatment-emergent skin rash has been associated with nivolumab. The majority of cases of rash have been mild in severity and self-limited, with or without pruritus.

A dermatologist should evaluate persistent and/or severe rash or pruritus. A biopsy should be performed unless contraindicated. Low-grade rash and pruritus irAEs have been treated with symptomatic therapy (e.g., antihistamines). Topical or parenteral corticosteroids may be required for more severe symptoms.

Table 5: Management of Skin Rash

Grade	Intervention
\leq Grade 1	No change in dose
Grade 2	Continue protocol therapy and monitor.
Grade 3	Omit dose of nivolumab and cabozantinib until $<$ grade 1.
Grade 4	Discontinue nivolumab and hold cabozantinib If the subject is unequivocally deriving clinical benefit, the subject may be able to resume cabozantinib at one dose level below prior dose once resolves to grade ≤ 1 .

. Patients with bullous lesions must be evaluated for vasculitis, Steven-Johnson syndrome,

Grade	Intervention
	
TEN, and autoimmune bullous disease including oral lesions of bullous pemphigus/pemphigoid.
 
Pruritus may occur with or without skin rash and should be treated symptomatically.Note skin rash typically occurs early and may be followed by additional events particularly during steroid taper.

